3.3 Subject Data and Study Conduct

3.3.1 *Subject Disposition*

Counts and percentages of patients who were screened (signed informed consent), discontinued early during screening (screen failures), and randomized/enrolled will be summarized in total based on all screened patients. Reasons for screen failure will also be summarized, including those due to the COVID-19 pandemic.

Counts and percentages of patients who were randomized to Group 1 and Group 2 and enrolled to Group 3, discontinued early from the study, and completed the study will be summarized

based on the ITT Population. Reasons for early discontinuation will also be summarized, including those due to the COVID-19 pandemic.

3.3.2 Protocol Deviations

Counts and percentages of patients with CSR-reportable protocol deviations by deviation category will be summarized based on the ITT Population. Protocol deviations related to COVID-19 may also be summarized.

3.3.3 Analysis Populations

Counts and percentages of patients in each analysis population will be summarized based on the ITT Population. Reasons for exclusion from each analysis population may also be summarized.

3.3.4 Demographic and Baseline Characteristics

Demographic characteristics (age, gender, etc.) and other baseline characteristics, including transplant characteristics, will be summarized for the ITT Population and repeated for other analysis populations (if different than the ITT Population).

The following demographic and baseline characteristics will be summarized:

- Age (years) at Informed Consent
- Sex
- Childbearing potential
- Race
- Ethnicity
- Height at screening (cm)
- Weight at screening (kg)
- Body mass index (BMI) (kg/m^2) at screening and BMI categories ($<30 \text{ kg}/\text{m}^2$, $\geq 30 \text{ kg}/\text{m}^2$)
- Baseline CMV quantitative PCR result
- Degree of human leukocyte antigen mismatch
- Use of induction therapy or not
- Relation of donor to patient
- Donor CMV serology
- ABO incompatibility
- Donor living status
- Warm ischemia time
- Cold ischemia time and unit
- Use of laparoscopy or not
- Side of kidney

3.3.5 Medical History

Medical history will be coded to system organ class and preferred term using the Medical Dictionary for Regulatory Activities (MedDRA) version 22.0. Counts and percentages of patients with medical history by system organ class and preferred term will be summarized based on the Safety Population for all medical history that did end prior to 14 days before Day 0.

3.3.6 Concomitant Medications

Concomitant medications will be coded to anatomical therapeutic chemical (ATC) class and preferred term using the World Health Organization (WHO) Drug Dictionary version March 2019G B3. For summary purposes, medications will be considered prior medications if they stopped within 14 day of Day 0 and prior to the first dose of study drug, and concomitant medications if they were taken at any time after the first dose of study drug (i.e. started prior to the first dose of study drug and were ongoing or started after the first dose of study drug).

Counts and percentages of patients taking prior and concomitant medications by ATC class and preferred term will be summarized based on the Safety Population.

3.3.7 Study Drug Exposure

The number of doses of study drug taken (0, 1, 2, 3+) will be summarized for the Safety Population.

3.4 Endpoint Assessment

The mITT Population will be used for all endpoint analyses related to efficacy, the Safety Population for all endpoint analyses related to safety, and the Immunogenicity Population for all endpoint analyses related to immunogenicity. The results of the study will be analyzed descriptively. However, should the results be favorable, subgroup analyses and additional analyses may be performed based on patient characteristics, transplant characteristics, number and timing of vaccinations, or use of immunosuppression to identify factors influencing vaccine response.

3.4.1 Primary Endpoints

3.4.1.1 Adverse Events (AEs)

AEs will be captured from the date of informed consent through study completion. All AEs will be coded to system organ class and preferred term using the MedDRA version 22.0 and analyzed using the Safety Population. A treatment-emergent adverse event (TEAE) is defined as an adverse event with a start date and time on or after the first administration of study drug and up to 30 days past the last administration of study drug, or after 30 days past last dose and meeting one of the following criteria:

- Serious AE (SAE)
- AE of special interest post-transplant
- AE related to study medication
- AE related to HLA sensitization

Adverse events of special interest post-transplant are graft rejection, CMV syndrome, and CMV disease.

An overview of AEs will be provided including counts and percentages of patients with the following:

- Any AEs
- Any TEAEs
- Any Grade 3 (severe) or higher TEAEs
- Any Grade 3 (severe) or higher TEAEs related to study medication

- Any TEAEs related to study medication
- Any TEAEs of special interest post-transplant
- Any TEAEs of special interest post-transplant and related to study medication
- Any serious AEs (SAEs)
- Any treatment-emergent serious AEs (TE-SAEs)
- Any TEAEs leading to discontinuation of study medication
- Any TEAEs related to study medication leading to discontinuation of study medication
- Any TEAEs related to COVID-19
- Most frequently reported adverse events related to study medication

Both the pre-transplant and post-transplant adverse events and adverse events of above categories will be included in the table summary. The post-transplant adverse event will be summarized by treatment group for Groups 1 and 2 and open-label HB-101 for Group 3.

Counts and percentages of patients will also be presented by system organ class and preferred term for each of the categories in the overview. Counts and percentages of most frequently reported adverse events and most frequently reported adverse events related to study medication may also be displayed in separate tables.

Listings will be presented specifically for SAEs and TEAEs leading to discontinuation of study drug.

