The patient will complete and conclude the study on whichever day of the study one of the following events first occurs:

- When the patient completes the study follow-up (12 months post-transplant).
- If for some reason kidney transplant has not occurred by 12 months after the first dose of study drug (HB-101 or placebo).
- If the patient experiences graft failure requiring removal of the transplanted organ or returns to dialysis.
- If the patient is withdrawn or withdraws from the study.
- If the patient is lost to follow-up.
- If the patient dies.

The total duration of the study for each patient participating in the study will be approximately 15 months.

The dosing schedule relative to transplantation is listed in Table 1.

Study drug is defined as either HB-101 or placebo.

Table 1 Timing of Kidney Transplant vs. Study Drug (HB-101 or Placebo) Injection, Where Day 0 is the Day of First Dose of Study Drug

Timing of Kidney Transplant	Number of Injections Planned	Timing of Study Drug Injection
Prior to Day 34	1*	Day 0
Between Day 35 and Day 62	2	Day 0 and Day 28**
Between Day 63 and Day 90 or Between Day 91 and Day 120	3	Day 0, Day 28**, and Day 56** or Day 84**
*Patients who received only 1 dose of study drug will be excluded from the mITT Population for efficacy analysis. **After Day 0 dose administration, a timeframe of ± 7 days from scheduled day of dosing is allowed. mITT = modified Intent-to-Treat; Day 0 = day of first dose of study drug; Day 28 = 28 days after the first dose of study drug; Day 34 = 34 days after the first dose of study drug; Day 35 = 35 days after the first dose of study drug; Day 56 = 56 days after the first dose of study drug; Day 62 = 62 days after the first dose of study drug; Day 63 = 63 days after the first dose of study drug; Day 84 = 84 days after the first dose of study drug; Day 90 = 90 days after the first dose of study drug; Day 91 = 91 days after the first dose of study drug; Day 120 = 120 days after the first dose of study drug.		

In brief, it is the intent of this study to administer up to 3 doses of study drug (HB-101 or placebo) prior to transplantation and within proximity to the time of transplantation. However, 2 doses of study drug before transplant will be sufficient for the patients to be included in the efficacy analyses if a third dose of study drug is not feasible due to transplantation timelines. Patients will not receive study drug after transplantation.

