After Day 0 dose administration, the subsequent study drug administration(s) should be given 28 days (± 7 days) apart.

Patients whose planned transplantation is less than 35 days from the planned first study drug (HB-101 or placebo) injection should not be enrolled.

A minimum of 7 days (± 2 days) must be planned between the last dose of study drug and transplantation, unless agreed otherwise between the sponsor and investigator on a case-by-case basis.

Patients whose planned transplantation is no longer than 4 months from the time of the first study drug (HB-101 or placebo) injection should be enrolled. Changes in transplantation timelines will not result in patient withdrawal from the study. In case of delayed transplantation, additional study drug injections prior to transplantation can be discussed with the sponsor or sponsor designee (who should be blinded). The maximum allowed number of patients receiving additional study drug injections prior to transplantation will be capped at 10 patients (less than 10% of planned sample size).

For Groups 1 and 2, in the event that the living donor is not available and a kidney from a CMV seropositive (+) deceased donor becomes available, the patient can continue in the study after transplantation. For Group 3, in the event that the living donor is not available and a kidney from a deceased donor becomes available, the patient can continue in the study after transplantation.

The additional study drug booster will be administered at least 7 days (± 2 days) prior to the scheduled transplantation. This allows maximal protection against CMV prior to the transplant. Blood collection for immunogenicity will be performed prior to each study drug booster

administered. Immunogenicity will not be used to determine the administration of a booster as these results would be unblinding; instead, reactogenicity will be reviewed and the investigator and sponsor may decide not to administer the booster if there is evidence of increasing reactions with increasing number of vaccinations. The number and timing of vaccinations versus transplantation will be described in the descriptive analyses.

The schedule of events and Immunogenicity analysis and time points are listed in Appendix A.

2.2.2 *Randomization and Blinding*

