2.3 Study Endpoints

2.3.1 *Primary Endpoints*

For objective of assessing the safety and reactogenicity of HB-101, the primary endpoints are

- Incidence and severity of Adverse events (AEs), serious adverse events (SAEs), and changes in laboratory values
- Incidence and severity of localized or generalized injection site reactions

For objective of assessing the immunogenicity of HB-101, the primary endpoints are descriptive central statistics of the following immunogenicity parameters:

- CMV Neutralization (neut)
- CMV Enzyme-linked immunospot (ELISPOT) phosphoprotein 65 Kd (pp65)
- CMV ELISPOT gB

2.3.2 *Secondary Efficacy Endpoints*

- Incidence and time to clinically significant CMV infection, CMV disease, and CMV syndrome after transplant
- Incidence and time to CMV viremia requiring anti-viral therapy after transplant
- Incidence and duration (in days) of anti-CMV therapy courses (at therapeutic doses) required after transplant
- Incidence and time to quantifiable CMV DNAemia , peak CMV DNAemia level, and duration of CMV DNAemia above the limit of quantitation after transplant
- Incidence and time to graft failure and organ rejection after transplant

2.3.3 *Exploratory Efficacy Endpoints*

Descriptive central statistics of the following immunogenicity parameters:

- CMV Intracellular cytokine staining (ICS) pp65
- CMV ICS gB
- LCMV ELISPOT nucleoprotein (NP)

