Record adverse events Record adverse events -Adverse events, regardless of causality, should be recorded up through 30 days after the last injection of study drug. -Adverse events considered related to the study drug should be recorded from 31 days after the last injection of study drug up through the End of Study Visit.	<-----X-----> Ongoing during study				<-----X-----> Ongoing during study			
Record SAEs	<-----X-----> Ongoing during study				<-----X-----> Ongoing during study			
Concomitant medications related to SAEs	<-----X-----> Ongoing during study				<-----X-----> Ongoing during study			
Concomitant medications of special interest -Anti-virals and immunosuppressants, non-study vaccines, granulocyte colony-stimulating factor, erythropoietin, and transfusions of blood product taken 7 days prior to and after transplant.	<-----X-----> Ongoing during study				<-----X-----> Ongoing during study			
Record adverse events of special interest:	<-----X-----> Ongoing during study				<-----X-----> Ongoing during study			
Graft rejection assessments	Transplant Follow-up visits per institutional standard.							X

CMV disease and syndrome assessments	Transplant Follow-up visits per institutional standard.							X
Blood sample for CMV PCR local testing: ⁶								
Patients to be followed preemptively post-transplant for the first 16 weeks after transplant.	X	X	X	X	X	X	X	X
Patients to be treated prophylactically with anti-virals post-transplant.	Time points following institution's standard of care.				X	X	X	X
Blood sample for central CMV PCR analysis	Study site personnel will draw the patient's blood sample for central CMV PCR analysis when local CMV PCR testing is conducted at the institution.				X	X	X	X

1. Time window of follow-up visits after transplant is ± 7 days.
2. Follow-up visits will occur per institutional standards of post-transplant clinical monitoring after discussion with the sponsor.
3. Per Section 6.4, the End of Study Visit is also the 12 months post-transplant follow-up visit.
4. During the study, it is possible that the time windows of study visits and assessments will be redundant. If time window is ± 2 weeks, assessments should NOT be duplicated.
5. There is a ± 7 day window on assessments during the post-transplant Follow-Up Period, to take into account public or religious holidays or weather, if not explicitly specified otherwise.
6. Only 1 post-transplant CMV management strategy will be followed (preemptively or prophylactically).

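### The TEAE definition pools an all-cause window around vaccination with selected events up to 12 months after transplant, so the pooled TEAE totals dilute an early difference between arms and can be partly offset by efficacy

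*SAP*

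**What the plan says.** Section 3.4.1.1 builds the TEAE in two parts. The first is all-cause, from first dose "up to 30 days past the last administration of study drug". The second has no end date: it takes any event "or after 30 days past last dose and meeting one of the following criteria", and the criteria are an SAE, an event of special interest after transplant, a related event, or an event related to HLA sensitization. The special-interest list is short: "Adverse events of special interest post-transplant are graft rejection, CMV syndrome, and CMV disease".

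Those same outcomes appear in section 2.3.2 as secondary efficacy endpoints: "Incidence and time to clinically significant CMV infection, CMV disease, and CMV syndrome after transplant" and "Incidence and time to graft failure and organ rejection after transplant".

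Section 2.2.1 follows patients to 12 months after transplant and sets the gap before surgery: "A minimum of 7 days (± 2 days) must be planned between the last dose of study drug and transplantation" (exceptions can be agreed case by case). Appendix A limits late collection of ordinary events: "Adverse events considered related to the study drug should be recorded from 31 days after the last injection of study drug" to the End of Study Visit, while SAEs and events of special interest are recorded throughout.

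The overview in section 3.4.1.1 has rows for any AE, any TEAE, Grade 3 or higher TEAEs, related TEAEs, special-interest TEAEs, SAEs, treatment-emergent SAEs and discontinuations. Each is also broken down by SOC and preferred term. The section says that events before and after transplant will both be in the summary, but it states a display by treatment group only for the post-transplant events.

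**The concern.** Safety is a primary objective (section 2.1.1), and the incidence and severity of AEs and SAEs is a primary endpoint (section 2.3.1). A reader who wants to know whether HB-101 causes more events than placebo around vaccination will look at the TEAE totals. No planned row gives all-cause events in that period without the late additions.

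Three consequences follow:

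- A patient with both an early and a late event counts once. The more patients have a late qualifying event, the less the total can show an early difference.
- CMV syndrome, CMV disease and rejection are in the numerator of a safety rate. If the vaccine prevents any of them, its TEAE rate falls for a reason unrelated to tolerability. Applying the same definition in both arms does not remove this, because the effect itself differs by arm.
- Every SAE after first dose qualifies, whenever it occurs, so the treatment-emergent SAE row does almost no filtering by time.

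**Working it through.** The SAP states no event rate, effect size or power for this point, so there is no figure of its own to reproduce. All rates below are assumptions.

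**1. Length of the two parts.** Inputs: Table 1 with nominal dosing (last dose on Day 28, 56 or 84), its transplant-day ranges, and 12 months taken as 365 days. The all-cause part ends at last dose + 30. Late days = (transplant day + 365) − (last dose + 30).

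| Last dose | Transplant day | All-cause part ends | Late days | Late share of time from first dose to end of study |
|---|---|---|---|---|
| 28 | 35 | 58 | 342 | 342/400 = 85.5% |
| 28 | 62 | 58 | 369 | 369/427 = 86.4% |
| 56 | 63 | 86 | 342 | 342/428 = 79.9% |
| 56 | 90 | 86 | 369 | 369/455 = 81.1% |
| 84 | 91 | 114 | 342 | 342/456 = 75.0% |
| 84 | 120 | 114 | 371 | 371/485 = 76.5% |

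The late part is thus about 75% to 86% of time on study for patients with 2 or 3 doses. This is a share of time; it does not give the rate of late events.

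**2. Dilution.** Let p be the risk of an event in the all-cause part and b the risk of a late qualifying event, independent of each other and with b equal in both arms. Then P(any TEAE) = 1 − (1 − p)(1 − b), and the difference between arms is (p_HB-101 − p_placebo)(1 − b). Assume p = 30% on placebo and 50% on HB-101, a 20-point excess. The last column lets the vaccine cut late events by an assumed 20%, so that b on HB-101 is 0.8b.

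| b | Placebo | HB-101 | Difference (points) | Difference if HB-101 cuts b by 20% (points) |
|---|---|---|---|---|
| 20% | 1 − 0.7×0.8 = 44% | 1 − 0.5×0.8 = 60% | 16 | 58 − 44 = 14 |
| 30% | 51% | 65% | 14 | 62 − 51 = 11 |
| 50% | 65% | 75% | 10 | 70 − 65 = 5 |
| 70% | 79% | 85% | 6 | 78 − 79 = −1 |

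The factor 1 − b does not depend on the starting risks. Each pooled row has its own b: for treatment-emergent SAEs, for example, b is the risk of a late SAE.

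**3. Treatment-emergent SAEs against any SAEs.** An SAE up to 30 days after last dose qualifies as all-cause; a later one qualifies because it is serious. In the Safety Population the two rows can differ only by SAEs before first dose, and Appendix A marks SAE recording only from Day 0.

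**4. Would a plain 30-day cut-off be enough?** With nominal dosing, transplant falls within 30 days of the last dose on Days 35–58, 63–86 and 91–114, which is 24 + 24 + 24 = 72 of the 28 + 28 + 30 = 86 transplant days in Table 1 (84%). With a 7-day gap, 30 − 7 = 23 days after transplant lie inside the window. A 30-day cut-off alone would leave events around surgery in the vaccination window.

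**The case against.** The strongest defence is that the rule follows data collection. After 30 days from the last injection, Appendix A collects essentially related events, SAEs and events of special interest, which is nearly the set that the definition adds. The rule is prespecified and identical in both blinded arms, and section 3.1.4 plans no formal hypothesis testing. This explains the definition, but it does not turn the pooled total into a measure of risk around vaccination.

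The second defence stands and limits the point. Rows for related events, the special-interest row, SOC/PT tables, injection-site summaries (section 3.4.1.3), laboratory values and SAE listings would still show much of a signal. An excess in a specific early event is not diluted by rejection or CMV disease under another preferred term. Two limits remain: related rows rest on causality opinion, and SOC/PT tables of TEAEs use the same pooled period.

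The third defence is the sentence on events before and after transplant. A clear pre-transplant column would help, since that period is exposed to vaccine and free of surgery. The sentence does not commit to one by arm, and a split at transplant alone would put the remaining post-dose days together with the following year.

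A reader might go further and infer that transplant events swamp the TEAE rate, that it mainly measures the post-transplant year, or that it hides vaccine harm. The SAP does not support this. It gives no rate of SAEs, rejection or CMV disease, and at b = 20% most of the excess survives. One can construct a case in which the excess vanishes: early risks of 40% and 55% with late risks of 60% and 45% give 1 − 0.60×0.40 = 76.0% and 1 − 0.45×0.55 = 75.25%. If the late fall is due to CMV events, at least 15% of patients must have CMV syndrome or disease as their only late qualifying event, and all of these must be prevented. Viremia alone is not an event of special interest, and all patients are managed preemptively or prophylactically. Nothing in the SAP makes that size likely.

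**Conclusion.** The point holds for the pooled totals: any TEAE, Grade 3 or higher TEAE and treatment-emergent SAE. They shrink an early difference by 1 − b. For an assumed b of 20% to 70%, a 20-point excess becomes 16 to 6 points. This rests on early and late events being independent and on b being equal in the arms. If the vaccine also lowers late events, the difference shrinks further; with an assumed 20% reduction it is 14 to −1 points over the same range. The direction follows from the definition, but the size depends on rates that the SAP does not give.

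The near-duplication of the two SAE rows needs no assumed rate. It follows from the definition, apart from any SAE before first dose. The claim does not extend to the related-event, SOC/PT, special-interest or injection-site outputs. This is a presentation weakness on a primary objective and is worth correcting before database lock.

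**What to change.** Keep every collected event, and present the TEAE, Grade 3 or higher and SAE rows by arm in three periods:

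- (a) first dose to the earlier of transplant or 30 days after last dose;
- (b) transplant to 30 days after last dose, where transplant comes first;
- (c) later than 30 days after last dose, for SAEs, related events and HLA-sensitization events.

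Show CMV syndrome, CMV disease and graft rejection in their own rows, outside the any-TEAE total. Keep the any-SAE row complete, so that a serious CMV or rejection event does not drop out of the safety tables. Reword the sentence on events before and after transplant to match.

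The cost is SAP wording and a few more table rows from dates already collected. The reader must look at more rows, and because a patient can count in more than one period, the period counts will not add up to the number of patients with any event. A footnote should say so.

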3.1.3 Summary Statistics

Continuous variables will be summarized by using the number of non-missing observations, arithmetic mean, standard deviation, median, minimum, and maximum values as descriptive statistics. Categorical variables will be summarized by using the frequency count and the percentage of patients in each category as descriptive statistics. All data will also be listed.

Within each population, results will be presented according to treatment arm and total for Groups 1 and 2 and open-label HB-101 for Group 3 and total for all the three groups unless specified otherwise. Results from Groups 1 and 2 and results from Group 3 will be displayed in separate outputs unless specified otherwise.

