3.1.4 Hypothesis Testing

There is no formal hypothesis testing for this study. This study is for an initial assessment of the safety and immunogenicity of the vaccine candidate.

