3.4.1.3 Injection Site Reactions

For assessing the safety and reactogenicity of HB-101, the incidence and severity of localized or generalized injection site reactions will be summarized by symptom type and by injection site and symptom type for the Safety Population.

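### Severity of adverse events is part of a primary endpoint, but the SAP specifies only one severity cut (Grade 3 or higher) to summarise it

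*SAP*

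**What the plan says.** Section 2.3.1 lists as a primary endpoint: "Incidence and severity of Adverse events (AEs), serious adverse events (SAEs), and changes in laboratory values".

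Section 3.4.1.1 analyses that endpoint. Among the overview categories, two concern severity: "Any Grade 3 (severe) or higher TEAEs" and "Any Grade 3 (severe) or higher TEAEs related to study medication". On the detailed tables it says: "Counts and percentages of patients will also be presented by system organ class and preferred term for each of the categories in the overview". On listings: "Listings will be presented specifically for SAEs and TEAEs leading to discontinuation of study drug".

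Three other statements bear on the point:

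- Section 3.4.1.3, on the companion primary endpoint, says that "the incidence and severity of localized or generalized injection site reactions will be summarized by symptom type".
- Section 3.1.3 says "All data will also be listed".
- Section 3.1.4 says "There is no formal hypothesis testing for this study".

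**The concern.** The endpoint names severity, which is recorded on a graded scale, but the specified analysis reduces it to whether a patient had an event at or above Grade 3. Two kinds of information drop out of the by-arm summaries. Below the cut, mild and moderate events are not distinguished. Above it, Grade 3 is not distinguished from anything worse, and no overview row isolates TEAEs with a fatal outcome.

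This matters because the study's stated purpose is an initial assessment of safety and immunogenicity, with placebo controls in Groups 1 and 2. If HB-101 made non-serious events more intense without making more patients report an event, and without taking more of them to Grade 3, the specified tables would show the arms as alike.

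**Working it through.** There is no planned figure to reproduce: the SAP states no AE rates and plans no test on AEs. The check compares the text, then works out what the specified rows can determine.

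**1. Where AE severity is summarised.**

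| SAP section | Output | Severity information |
|---|---|---|
| 3.4.1.1 overview | Grade 3 or higher, all TEAEs and related TEAEs | One cut |
| 3.4.1.1 SOC/PT tables | Same categories as the overview | The same cut |
| 3.4.1.1 SAE rows, tables and listing | Serious events | Seriousness, not grade |
| 3.4.1.2 laboratory data | Values, changes, an optional liver-test shift table | No AE grade |
| 3.4.1.3 injection-site reactions | Local and generalised reactions by symptom type | Severity summarised, for this endpoint only |
| 3.5 vital signs and physical examination | Descriptive summaries | No AE grade |

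No section specifies AEs by grade or by maximum grade.

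**2. What the rows determine.** Write p0, p1, ..., p5 for the proportions of patients in an arm whose worst TEAE is none, Grade 1, ..., Grade 5. The SAP does not define its grading scale. Levels above 3 are inferred from the wording of the Grade 3 row, and a top level of 5 is assumed here.

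- Any TEAE = 1 − p0.
- Grade 3 or higher = p3 + p4 + p5.
- Their difference = p1 + p2.

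The split of p1 + p2 and the split of p3 + p4 + p5 are left open.

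**3. Illustration.** These rates are assumed and do not come from the SAP.

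| Worst grade per patient | None | 1 | 2 | 3 | 4 | 5 |
|---|---|---|---|---|---|---|
| HB-101 | 20% | 20% | 45% | 12% | 2% | 1% |
| Placebo | 20% | 50% | 15% | 15% | 0% | 0% |

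Specified rows:

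- Any TEAE: 100 − 20 = 80% in both arms.
- Grade 3 or higher: 12 + 2 + 1 = 15% on HB-101 and 15 + 0 + 0 = 15% on placebo.

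Not in any specified severity row:

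- Grade 2 or higher: 45 + 12 + 2 + 1 = 60% on HB-101 and 15 + 15 = 30% on placebo.
- Grade 4 or 5: 2 + 1 = 3% on HB-101 and 0% on placebo.

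From the two specified rows alone, Grade 2 or higher in either arm could lie anywhere from 15% (everyone below the cut at Grade 1) to 80% (everyone below the cut at Grade 2). The width of that interval, 80 − 15 = 65 points, is p1 + p2: the share of patients for whom the table says only that the worst event was below Grade 3.

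**4. What is covered elsewhere.**

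- *Reactogenicity.* Section 3.4.1.3 covers generalised as well as local reactions, and the schedule in Appendix A describes the post-dose examination as covering both local and general symptoms. The mild-to-moderate gap therefore concerns AEs outside those reactions.
- *Deaths.* Section 3.4.1.1 provides SAE and treatment-emergent SAE counts, SOC/PT tables for both, and an SAE listing. Death ends participation (Section 2.2.1), and reasons for early discontinuation are summarised (Section 3.3.1), by arm under Section 3.1.3. Fatal events can thus be found, although the SAE tables pool them with other SAEs.

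**The case against.** The strongest reply has four parts.

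*The main risk is already covered.* A vaccine's mild-to-moderate effect would be expected mainly in reactogenicity, which has its own severity summary. This stands and narrows the point to other AEs. A reader might infer that graded systemic reactions go unsummarised altogether; Section 3.4.1.3 rules that out.

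*Deaths are not hidden.* This largely stands. A reader might infer that a death would be lost in the Grade 3 row, but the SAE outputs and discontinuation reasons would show it. What remains is that no single row counts TEAEs leading to death by arm.

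*The list may not be complete.* The overview is introduced in open-ended terms, all data are to be listed, and Sections 4.1 and 5 refer to output templates and programming specifications that are not at hand. One therefore cannot say that the grades will never be tabulated, only that the SAP does not specify it. A patient listing is not a by-arm summary, and unseen templates do not fix the analysis of a primary endpoint.

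*Nothing is tested, so nothing is lost.* A reader might want to express the single cut as lost statistical power. The documents do not support that: Section 3.1.4 excludes formal testing, the remedy is a table rather than a test, and any such figure would depend on assumed grade frequencies. But a descriptive study depends on its summary tables, so the incomplete summary still matters.

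**Conclusion.** The point holds in a limited form. The SAP names AE severity in a primary endpoint and specifies one cut to describe it. For AEs outside the local and generalised injection-site reactions, a difference between arms in mild versus moderate events would appear in no specified summary table, and grades above 3 are pooled with Grade 3.

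The severity is low. The study is descriptive, the individual grades should appear in listings, and reactogenicity and deaths are wholly or partly covered elsewhere. The size cannot be taken from the documents; the illustration shows only that a large difference could go unseen, not that one is likely. The conclusion rests on reading Section 3.4.1.1 as the specification of the AE tables. The part about pooled grades also assumes that the scale has levels above 3, as the row's wording implies.

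**What to change.** In Section 3.4.1.1:

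- Add: *TEAEs and related TEAEs will be tabulated by maximum grade per patient, using each level of the trial's grading scale, overall and by system organ class and preferred term, by arm for Groups 1 and 2 and for Group 3.* Refer to the trial's own scale rather than writing in a fixed set of grades, since the SAP does not define it.
- Add an overview row for TEAEs leading to death.
- Keep both Grade 3 or higher rows.

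The cost is a short wording change and one or two standard tables; the downside is longer output. No new data should be needed, because the existing rows already require a grade for each event.
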